### **Intervention Group 2: (70 seniors (10 of these are calibration patients exclusively)).**

Seniors who are randomly assigned to the intervention group 2 will continue receiving regular dental care under the standard clinic operation and will also be invited to participate in an individual-based education activity over a 12 month period. The clinic visits will last for 1 hour each time and follow the guidelines established by TUKSoD to provide oral hygiene instruction using a Motivational Interviewing approach. Tailored education will be based on review of health related information to be extracted from medical (systemic diseases), dental chart (oral hygiene behaviors) and patient interview at time of initial examination. Seniors in this group will also receive basic preventative care (dental cleanings, fluoride varnish application (high caries risk individuals only) or referral to a supervised brushing program with high concentration fluoride under the care of the dentist at Kleinlife if needed. All individual based preventative activities will be provided by a Public Health Hygienist, and 3 dental visits will be conducted for subjects in this group during the course of a 18 month period. Baseline intake forms to assess changes in main behavioral outcomes will be administered before the first home based education session, at each follow up visit and after 18 months.

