### 1) Abstract of the study

**Introduction:** Older adults have been described as one of the most underserved and vulnerable groups, who are at the highest risk for coronal and root caries, especially because more elderly adults are retaining their teeth. The Northeast Philadelphia KleinLife site is an important destination for the region's Jewish population comprising of at least 6500 seniors, and assisting more than 4500 seniors through food security programs. Recently, Temple University Kornberg School of Dentistry (TUKSoD) purchased the dental center at the facility to expand the services provided to these underserved population and improve their oral health. The study aims to assess the efficacy of an oral health education group based activity versus an individual based oral health education activity in terms of changes in oral health related quality of life (OHRQoL), self-efficacy and oral health knowledge. **Methods:** A sample of 190 senior members will be invited to participate in the trial. Potential subjects will be obtained in person through the ongoing flow of patients at TUKSoD Clinic at Kleinlife and the dental school. Seniors who consent to participate in the study will be randomly allocated to one of the 3 groups (Control: subjects will continue receiving regular dental care at the clinic, Intervention 1: subjects will continue receiving regular dental care at the clinic and be invited to participate in 2 group based education sessions during a 12 month period, and Intervention 2: subjects will continue receiving regular dental care at the clinic and be invited to participate in an individual-based education and prevention activity over a 18 month period. Randomization will be determined according to a predetermined random sequence, and neither the patient nor the research staff will be aware of the randomization outcome until after the patient has agreed to participate. Subjects who consent to participate will be entered into a raffle to receive a \$350-dollar visa gift card, if they complete the baseline and follow up assessments. The OHIP-14 will be used to assess OHRQoL, and self-efficacy scores will be the primary outcomes. Initially, we will assess the differences between the interventions and control using 2-sample *t*-tests. The main analysis will be based on linear mixed-effects models for repeated measures (using the OHIP 14 and self-efficacy scores as continuous outcome variables) to assess differences between intervention and control groups. Similar analyses will be conducted for secondary outcome measures. Statistical significance will be set at  $p < .05$ .

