### **4) Objectives**

- **Primary Objective:**

The objective of this study is to test the efficacy of an oral health education group based activity versus an individual oral health education activity in terms of changes in oral health related quality of life (OHRQoL), self-efficacy and oral health knowledge.

- **Secondary Objective**

The secondary objective of this study is:

a) To assess differences among intervention and control groups by senior's oral health knowledge.

- **Overall Hypotheses**

Ho: There are no significant differences in the selected behavioral outcome measures between the interventions, either group-based or individual based education and the control.

Ho: The two educational interventions are not equivalent in the selected behavioral outcome measures.

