## ORAL HEALTH EDUCATION SENIORS

The objective of this study is to test the efficacy of an oral health education group based activity versus an individual based oral health education activity in terms of changes in oral health related quality of life (OHRQoL), and self-efficacy among seniors at Kleinlife and at the Dental School.

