### **Control Group: (60 seniors).**

Seniors who are randomly assigned to the control group will continue receiving regular dental care under the standard clinic operation. Subjects in this group will complete intake forms to assess main behavioral outcomes, at baseline and after 12 months. No other activities will be conducted in this group.

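### Group 2 is assigned preventive care as well as individual education, but the objective and hypotheses name education only; its contrasts support a claim about the package, not about individual education alone

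*Combined protocol and SAP*

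**What the plan says.** **Objective.** The aim sentence of the abstract is to "assess the efficacy of an oral health education group based activity versus an individual based oral health education activity". Section 4 (Objectives) says the study will "test the efficacy of an oral health education group based activity versus an individual oral health education activity". The end of section 5 and the Study Procedure text in section 7(d) both say "test the efficacy of an oral health education group based activity versus an individual based oral health education activity". None of the four mentions preventive care.

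**Hypotheses (section 4).** One concerns differences "between the interventions, either group-based or individual based education and the control". The other reads "The two educational interventions are not equivalent in the selected behavioral outcome measures". Both call the arms education.

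**Arms (section 7(d)).** All three arms keep regular dental care.
- Control has nothing further.
- Group 1 is invited to two one-hour group sessions that follow a published curriculum.
- Group 2 is invited to individual education using Motivational Interviewing, tailored from the chart and an interview. The description then continues: "Seniors in this group will also receive basic preventative care". This covers cleanings, varnish for high caries risk only, or a referral to supervised brushing with high-concentration fluoride if needed. A public health hygienist delivers the preventive activities.

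**Abstract, arm description.** Here Group 2 is an "individual-based education and prevention activity over a 18 month period", so prevention is acknowledged in that one place.

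**Data Analysis.** The primary outcomes are OHIP-14 and self-efficacy. The plan gives two-sample t-tests and then linear mixed models comparing the interventions with control. It has no term, adjustment or interpretive statement about preventive care.

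**The concern.** The question asked and the treatment assigned do not match. The objective asks what individual education does, relative to group education and to control. Group 2 is assigned that education together with clinical care.

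If Group 2 does better, the plan as worded leads to the conclusion that individual education worked. A clinic could then adopt one-to-one teaching without the cleanings and fluoride that may have contributed. If Group 2 and Group 1 look alike, that result would not be a clean statement about education either.

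The route is plausible for OHIP-14. Its items, listed in Appendix C, include painful aching in the mouth and discomfort when eating. Clinical care could change those answers with no effect of education at all.

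**Working it through.** The plan states no figure on this point and the documents give no size for a preventive-care effect, so the check compares the arms with the claims made about them.

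**Step 1: what each arm is assigned beyond regular dental care.**

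| Arm | Education | Preventive care listed |
|---|---|---|
| Control | none | none |
| Group 1 | group sessions | none |
| Group 2 | individual, Motivational Interviewing, tailored | cleanings; varnish if high caries risk; or supervised-brushing referral if needed |

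**Step 2: is the preventive care part of the education activity?** The Group 2 description first states the education activity and how it is tailored. It then says what the group will also receive. On the protocol's own wording the care is a second component. A cleaning or a varnish application is not education under any ordinary use of the word.

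**Step 3: what each contrast estimates.**
- Group 1 versus control: group education added to regular care. This matches the first hypothesis.
- Group 2 versus control: individual education plus preventive care, added to regular care. The first hypothesis calls this individual-based education.
- Group 2 versus Group 1: individual education plus preventive care, against group education. The objective and the second hypothesis call this a comparison of two educational interventions. Data Analysis names only intervention versus control, so this contrast rests on section 4.

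**Step 4: can the analysis separate the components?** No arm receives individual education without the preventive care, or the preventive care without individual education. The models compare assigned groups and include no term for care received. The components therefore cannot be separated, and what each Group 2 contrast estimates is the effect of the package.

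**Step 5: how far do the arms really differ in preventive care?** The documents do not say. Regular care continues in every arm and may include cleanings. Section 8 describes all clinical activities as part of normal dental treatment. Varnish and the brushing referral are conditional. The real difference could be small or nil. But the plan nowhere states that control and Group 1 will get the same preventive care, and the arm description reads as an addition to regular care.

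**The case against.** **The objective compares activities, and those activities are defined in the arm descriptions.** Section 7(d) restates the objective and then says that the activities are described below. On that reading the Group 2 activity already includes preventive care, and the abstract's arm description says so. This shows that the package is disclosed. It does not bring the package into the objective or the hypotheses, which say education. The abstract's own aim sentence omits prevention although its arm description includes it.

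**The clinical difference may be negligible.** This stands as a limit on size, for the reasons in step 5. The section 8 statement is about risk, however, and promises no equal provision across arms.

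**Comparing packages is a legitimate design.** Agreed. The arms need not change; the label on the comparison does.

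Three stronger readings are tempting, and the documents do not support them.
- A reader might infer that Motivational Interviewing, tailoring and the different curriculum also confound a comparison of education format. The protocol never claims to isolate format. Section 5 speaks of different types of education activity, and Motivational Interviewing and tailoring can fairly be seen as part of individual education. The point rests on preventive care alone.
- A reader might infer that the supervised-brushing referral would shift self-efficacy. It is a conditional referral, and nothing in the documents supports that pathway.
- A reader might infer that the Group 2 comparison is biased or invalid. It is a randomized comparison of the package and remains valid for that.

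**Conclusion.** The point holds in a limited form. Contrasts that include Group 2 are valid for individual Motivational Interviewing education plus preventive care. They do not support a conclusion about individual education alone, which is how the objective and both hypotheses are worded. Group 1 versus control is not touched.

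No size can be given. The documents contain no estimate of a preventive-care effect and no account of what preventive care the other two arms will actually receive, so the effect on results could be anything from nil upward and may well be small. The conclusion needs no assumption about that size. It rests only on reading the added care as additional to regular care, which is the natural sense of the Group 2 description.

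This is a cheap improvement to what the trial may claim. It is not grounds for changing the design.

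**What to change.** 1. In each statement of the objective (the abstract's aim sentence, section 4, the end of section 5, and Study Procedure in section 7(d)) and in both hypotheses, name Group 2 as *individual Motivational Interviewing education plus preventive care*. That is 4 + 2 = 6 text edits.
2. Add one sentence to Data Analysis: *Contrasts that include Group 2 estimate the effect of this package and will not be interpreted as an effect of individual education alone.*

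No arm, visit, form, sample size or model changes. The cost is a narrower claim: the trial could no longer report a Group 2 result as evidence about individual education by itself.

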### **Intervention Group 1: (60 seniors).**

Seniors who are randomly assigned to the intervention group 1 will continue receiving regular dental care under the standard clinic operation and will be invited to participate in 2 group based education activities over a 12 month period. The sessions will last for 1 hour each time and follow the guidelines established by the Oral Health America Curriculum. Baseline intake forms to assess changes in main behavioral outcomes will be administered before the first education session, after 6 months and after 12 months.

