### **Data Analysis:**

Initial analyses will be conducted to determine normality of distributions of the continuous variables, and any necessary transformations will be conducted. Primary outcomes will be the OHIP 14 and the self-efficacy scores. All eligible patients will be randomly assigned to 1 of the 3 groups described above. Although randomization should provide relatively comparable groups, demographic variables that differ between groups and are correlated with the primary outcomes will be used as covariates. Preliminary analysis will include measures of central tendency and dispersion, as well as an examination of the bivariate relationships among the primary and secondary outcome variables, potential moderators, and demographic characteristics.

Differences between the groups on baseline demographic, and psychological measures will be examined using  $\chi^2$  (Pearson) or Student's *t*-tests, as appropriate. Moreover, differences on the variables listed above among completers and drop-outs will also be explored. Intention to treat (ITT) analyses will then be conducted.

OHIP 14 and self-efficacy scores will be the primary outcomes. Initially, we will assess the differences between the interventions and control using 2-sample *t*-tests. The main analysis will be based on linear mixed-effects models for repeated measures (using the OHIP 14 and self-efficacy scores as continuous outcome variables) to assess differences between intervention and control groups. Similar analyses will be conducted for secondary outcome measures. Statistical significance will be set at  $p < .05$ .

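### After baseline the individual-education arm shares no stated assessment month with the other two arms, and no primary time point is named, so both comparisons involving that arm can be confounded with follow-up time

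*Combined protocol and SAP*

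**What the plan says.** The three arm descriptions under Study Procedure set three different schedules.

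- Control: "Subjects in this group will complete intake forms to assess main behavioral outcomes, at baseline and after 12 months".
- Intervention Group 1 (group sessions): the forms "will be administered before the first education session, after 6 months and after 12 months".
- Intervention Group 2 (individual sessions): the forms "will be administered before the first home based education session, at each follow up visit and after 18 months". On visits, the section says that "3 dental visits will be conducted for subjects in this group during the course of a 18 month period". It does not say in which months they fall.

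The length of the individual programme is given in two ways. The Intervention Group 2 section first describes an "individual-based education activity over a 12 month period" and then refers to 18 months twice. The Abstract describes an "individual-based education and prevention activity over a 18 month period".

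The primary objective (section 4) is to test a "group based activity versus an individual oral health education activity". In the Data Analysis section, "The main analysis will be based on linear mixed-effects models for repeated measures", preceded by two-sample t-tests. OHIP-14 and self-efficacy are the primary outcomes. Neither that section nor the Objectives or Abstract attaches a month to them, says whether time is categorical or continuous, or names the contrast to be tested.

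Table 1 (Study Timelines), whose dates are labelled approximate, puts recruitment and baseline in summer to fall 2017 and follow-up in spring to summer 2018.

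**The concern.** Randomisation makes the arms comparable at the same elapsed time. It does not protect a comparison of one arm at month 18 with another at month 12. All three arms continue regular dental care, so OHIP-14 and self-efficacy scores may move in every arm for reasons unrelated to the education. Any movement between months 12 and 18 would then be counted as a difference between individual and group education, or between individual education and control.

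What is at stake is the contrast the trial was designed to answer. Because neither a time point nor a model for time is fixed, its result would depend on when the individual visits happen to fall and on a modelling choice made later. Data never collected at a common month cannot be recovered in the analysis.

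**Working it through.** The documents give no power calculation, SD, drift or correlation, so there is no figure of the plan's own to reproduce. Steps 1, 2 and 5 use the documents, with the season dates in step 5 assumed. Steps 3 and 4 are illustrations on assumed values.

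**1. Stated assessment months**

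| Arm | Baseline | Stated months after baseline |
|---|---|---|
| Control | yes | 12 |
| Group | yes | 6, 12 |
| Individual | yes | 18, plus visits at unstated months |

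Control and group share month 12. Control and individual share none, and group and individual share none. An individual visit could fall at month 12, but nothing requires it.

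**2. What the mixed model can do.** With categorical time, month 18 is observed in one arm only, so no between-arm contrast can be estimated there. A month-12 contrast needs individual-arm data at month 12, which are not scheduled. With linear time, a contrast can be computed, but it is unbiased only if the trend shared by the arms is linear. Control has two time points, so its curvature cannot be checked.

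**3. Illustration: comparing last assessments (month 18 against month 12).** Assumptions: 60 per arm (the 10 calibration patients in the individual arm are excluded), full retention, no true effect, two-sided 5% test, shared drift of d SD from month 12 to month 18.

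SE = √(2/60) = 0.183 SD; rejection rate = Φ(d/SE − 1.96) + Φ(−d/SE − 1.96).

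| d (SD) | 0.05 | 0.1 | 0.2 | 0.3 |
|---|---|---|---|---|
| False-positive rate | 5.9% | 8.5% | 19.5% | 37.6% |

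With 48 per arm (20% loss assumed), the last three become 7.8%, 16.5% and 31.2%.

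**4. Illustration: mixed model with random intercept and linear time-by-arm term.** Total SD is 1, within-person correlation is ρ, and there are 60 per arm. The group arm is at months 0, 6 and 12. The individual arm is assumed at 0, 9 and 18.

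For three equally spaced times, the fitted slope is (last − first)/(time span). The shared trend is taken as a straight line to month 12. Slope difference per 12 months (group minus individual):

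- linear trend: 0;
- 0.2 SD by month 12, then flat: 0.2 − 0.2 × 12/18 = 0.067 SD;
- 0.3 SD by month 12, then flat: 0.3 − 0.3 × 12/18 = 0.10 SD;
- 0.2 SD by month 12, back to baseline by month 18: 0.2 − 0 = 0.20 SD.

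The sums of squared time deviations are 72 (group) and 162 (individual). So SE² = (1 − ρ) × 144 × (1/72 + 1/162)/60 = 0.0481 × (1 − ρ), which gives SE = 0.184, 0.155 and 0.120 at ρ = 0.3, 0.5 and 0.7.

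| Shared trend | ρ = 0.3 | ρ = 0.5 | ρ = 0.7 |
|---|---|---|---|
| Linear | 5.0% | 5.0% | 5.0% |
| 0.2 SD by month 12, then flat | 6.5% | 7.1% | 8.6% |
| 0.3 SD by month 12, then flat | 8.5% | 9.9% | 13.2% |
| 0.2 SD by month 12, back to 0 at month 18 | 19.3% | 25.2% | 38.4% |

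If the individual visits are assumed at 0, 6, 12 and 18 instead, the last two rows become 7.9%, 9.1%, 11.8% and 16.9%, 21.8%, 33.1%. These rates apply to the linear-time model only. With that visit pattern, a categorical-time contrast at month 12 would be free of drift.

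**5. Calendar.** Take summer as June to August and fall as September to November.

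- First possible enrolment, 1 June 2017, to end of follow-up, 31 August 2018: 15 months.
- Last enrolment, 30 November 2017, to 31 August 2018: 9 months.
- 18 months after those two enrolment dates: 1 December 2018 and 30 May 2019.

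No 18-month assessment fits for anyone, and month 12 does not fit for the last enrolled.

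**The case against.** The strongest reply is that this is a drafting conflict. The Intervention Group 2 section states both periods, and Table 1 has no room for 18 months. If the sponsor meant 12 months throughout, corrected wording and a named month-12 contrast might settle the matter at no cost. That may be so, but 18 months appears in the Abstract and twice in the arm description, so the text as it stands must still be changed.

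A second reply is that mixed models accommodate unequal assessment times. They do so only under an assumed shape for time, and the plan states none.

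Third, the false-positive rates rest on assumptions, and this stands as a limit on the size. The plan does not specify a last-visit test. A full return to baseline within six months is an extreme shape. Three visits plus an 18-month form may fit 0, 6, 12 and 18 better than 0, 9 and 18. The milder cases run from 5.9% to 8.6%. None of this supplies the missing common month or the missing time point.

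Finally, a month-12 contrast has a drawback. If the individual programme runs 18 months, month 12 compares a completed group programme with an unfinished individual one. That is a fair point, and the fix allows for it.

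**Conclusion.** The concern holds and should be settled before data collection. It is certain from the text that the individual arm has no stated post-baseline month in common with the other arms and that no primary time point or model for time is given. Group versus individual and individual versus control are affected; group versus control is not.

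The size of any bias is not known. It is nil under a linear shared trend in a linear-time model. In the illustrations with non-zero drift and 60 per arm, the false-positive rate runs from just above the nominal 5% to nearly 40%, depending on the assumed drift, correlation, visit months and analysis. Those figures show scale and are not estimates for this trial. The direction of the bias follows the direction of the drift.

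**What to change.** - Schedule a month-12 assessment in all three arms, timed from randomisation and with the same window.
- Name the month-12 time-by-arm contrast from the mixed model, with time categorical, as the primary comparison. Report any 18-month data from the individual arm as descriptive.
- If the individual period is reconciled as 18 months and the sponsor wants an end-of-programme comparison, use a common month-18 assessment in all three arms instead, with the contrast named at that month. The choice should be explicit, since it decides whether the individual programme is complete when it is compared.
- Reconcile the 12- and 18-month statements in the Abstract and the Intervention Group 2 section. Which period is intended is for the sponsor to say.
- Extend Table 1 to the last scheduled assessment of the last enrolled participant: about 30 November 2018 if month 12 is last, or about 30 May 2019 if any 18-month data are kept.

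The cost is at most one added in-person questionnaire contact for the 60 individual-arm participants, and none where a visit already falls at month 12. If month 18 is chosen, it is one contact for the 120 in the other two arms. Data collection runs about 3 months past Table 1 for month 12, or about 9 months if 18-month data are kept, and the manuscript date moves with it. No extra patients are needed.
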